#### 4.8 Site

A single site is planned for this trial: University of Pittsburgh, Pittsburgh, USA

## 5 STUDY POPULATION

### 5.1 Selection of the Study Population

#### 5.1.1 Composition

It is anticipated that the study population will be primarily composed of Caucasian and African-American women consistent with the primary racial and ethnic composition of patients at Magee-Womens Hospital of UPMC. Women of other racial and ethnic backgrounds will not be excluded. As this study will be assessing the pharmacokinetics of a vaginally applied product among pregnant women, only female participants will be enrolled.

### 5.1.2 Recruitment

Members of the research team including the Site PI will recruit potential participants during the antenatal period using IRB-approved materials.

### 5.2 Inclusion Criteria

Women must meet all of the following criteria (by self-report, unless otherwise indicated) to be eligible for inclusion in the study:

1. Age 18-45 years at screening and enrollment, inclusive, and verified per site standard operating procedure (SOP).
2. Willing and able to provide written informed consent for screening and enrollment
3. General good health as determined by the site Investigator of Record (IoR) or designee at Screening and Enrollment Visit
4. HIV-uninfected (per HIV Testing Algorithm, Appendix II)
5. HBsAg negative at Screening and Enrollment Visit or documented negative during this pregnancy
6. Pregnancy with the following characteristics:
  - Viable
  - Singleton
  - Without ultrasound evidence of significant fetal congenital anomaly (in the opinion of the IoR or designee)
  - Term (37 0/7 to 41 6/7 weeks, inclusive, with gestational dating criteria per SOP) at the time of planned cesarean section
  - Planned cesarean section
7. Normal Pap (or completed evaluation of abnormal Pap) in the 12 calendar months prior to screening per SOP
8. Willing to:
  - abstain from vaginal sex, anal sex, and receptive oral sex for at least two weeks after gel placement
  - abstain from intravaginal products and practices (including douching) during study participation
  - not participate in other drug or device study during study participation
  - participate as required by protocol, including study product administration, assessments and follow-up schedule

### 5.3 Exclusion Criteria

Women who meet any of the following criteria (by self-report, unless otherwise indicated) will be excluded from the study:

1. Maternal or fetal condition that necessitates urgent cesarean section (e.g. active labor, non-reassuring fetal heart tracing)
2. Documented rupture of the amniotic membranes, as defined in the SOP
3. Known maternal disease with predictable negative affect on placental function (e.g. hypertension, diabetes mellitus, collagen vascular disease, clinically significant maternal anemia)
4. Known placental/fetal abnormalities that could affect placental transfer (e.g. placental abruption, placenta previa, placenta accreta, intrauterine growth restriction, two vessel cord, etc.)
5. Serum creatinine at Screening and Enrollment Visit greater than 1.0 mg/dL
6. AST and/or ALT at screening greater than 1.5 ULN (upper limit of normal)
7. Current or recent (within 48 hours) use of vaginal medications at the Screening and Enrollment visit (per participant report)
8. Untreated sexually transmitted infection or (as applicable) exposure to partner's infection, including chlamydia, gonorrhea, trichomoniasis, non-gonococcal urethritis  
*Note: women diagnosed with an STI during screening or in the process of enrollment will be offered or referred for treatment in accordance with CDC guidelines. These participants will be eligible for enrollment once they have completed treatment(s) and are asymptomatic for the STI(s).*
9. Symptomatic vaginitis, including bacterial vaginosis and vulvovaginal candidiasis (participants with asymptomatic signs of bacterial vaginosis and/or yeast are still eligible for enrollment)
10. Participation in any other investigational drug or device trial within 30 days prior to enrollment visit
11. At screening or enrollment, any social or medical condition that, in the investigator's opinion, would preclude informed consent, make study participation unsafe, complicate interpretation of study outcome data, or otherwise interfere with achieving the study objectives

## **6 STUDY PRODUCT**

### **6.1 Regimen**

All study participants will receive a single vaginal dose of 4 grams of tenofovir 1% gel followed by 24 hours of intensive PK sampling.

### **6.2 Administration**

Four grams of tenofovir 1% gel will be administered vaginally, using the vaginal applicator provided, by the authorized clinician, approximately two hours prior to the expected time of cesarean section (optimally at least one hour prior to the collection of cord blood).

### **6.3 Study Product Formulation and Preparation**

Tenofovir gel is a clear, transparent viscous gel packaged in epoxy inner-lined aluminum tubes with white polyethylene screw caps equipped with a puncture tip. Each single-dose tube contains nominally 6 grams of tenofovir gel at a concentration of 1% (weight per weight) formulated in purified water with edetate disodium, citric acid, glycerin, methylparaben, propylparaben, and hydroxyethylcellulose, with pH adjusted between 4.0 and 5.0. The study gel is applied with a polyethylene applicator capable of administering a 4 gram dose. The product must be stored at 25°C (77°F) with excursions permitted to 15-30°C (59-86°F).

Immediately prior to application, the authorized clinician will fill the vaginal applicator by removing the cap from the tube of study gel, puncturing the metal seal on the tube with the pointed tip of the cap, screwing the end of the applicator onto the tube and slowly squeezing gel out of the tube and into the applicator. The plunger will stop when the applicator is full (contains the 4 grams of study product).

### **6.4 Study Product Supply and Accountability**

#### **6.4.1 Study Product Supply**

Tenofovir 1% gel and applicators will be provided by CONRAD (Arlington, VA). Tenofovir 1% gel is manufactured, packaged, labeled, analyzed and released by Gilead Sciences (Foster City, CA) under current good manufacturing practices (cGMP), 21 Code of Federal Regulation, conditions.

#### **6.4.2 Study Product Acquisition**

Tenofovir 1% gel and vaginal applicators will be available through the DAIDS Clinical Research Products Management Center. The Pharmacist of Record can obtain the

study product for this protocol by following the instructions in the *Pharmacy Guidelines and Instructions for DAIDS Clinical Trials Networks*.

### **6.4.3 Dispensing**

The tenofovir 1% gel tube for a study participant and a vaginal applicator will be dispensed only upon receipt of a written prescription from an authorized prescriber. The study product should be kept in the pharmacy until the day of the planned cesarean section.

### **6.4.4 Accountability**

The Pharmacist of Record is required to maintain complete records of all study products received from the DAIDS Clinical Research Products Management Center and subsequently dispensed. All unused study products must be returned to the DAIDS Clinical Research Products Management Center after the study is completed or terminated. The procedures to be followed are provided in the *Pharmacy Guidelines and Instructions for DAIDS Clinical Trials Networks*.

### **6.4.5 Retrieval of Unused Study Products**

Physician investigators and authorized study site staff must return any unused study product tubes and unadministered study product in applicators to the pharmacy.

## **6.5 Concomitant Medications and Procedures**

With the exception of those not permitted under inclusion/exclusion criteria, concomitant medications will be permitted. These include both prescription and non-prescription medications.

All concomitant medications reported throughout the course of the study will be recorded on the participant's chart on forms designated for that purpose. Inpatient medications (including medications for anesthesia, intravenous fluids, and others), prescription medications, over-the-counter preparations, vitamins and nutritional supplements, and herbal preparations will all be recorded as concomitant medications. Forms will include a place to record the time of administration for all medications up until 24 hours following the administration of the study gel.

### **6.5.1 Prohibited Medications and Practices**

Vaginal douching will not be permitted to protect the integrity of the lower genital tract and reduce the possibility of adverse events due to agents other than the study products. However, in the event that prohibited practices are reported following

administration of study gel, the protocol-specified visit schedule will continue for such participants for safety assessment through study exit. All concomitant medications will be recorded on Concomitant Medication Records.

Vaginal, anal, and receptive oral sex will not be permitted for at least two weeks following gel administration. Women will be advised to follow the instructions of their surgeon.

## **7 STUDY PROCEDURES**

The following should take place for study participants:

- Screening and Enrollment Visit
- Pharmacokinetic Measures (includes gel administration)
- 24-hour Evaluation
- Two Week Phone Call

### **7.1 Screening and Enrollment Visit**

The Screening and Enrollment Visit will occur approximately one to four weeks prior to the participant's scheduled C/S, but no more than four weeks before the expected date of cesarean section. This will allow the receipt of results for laboratory measures employed as components of screening.

Screening and Enrollment procedures are outlined below in Table 2: Screening and Enrollment Visit. If necessary, components of the Screening and Enrollment Visit may occur on different days. If necessary, components of the Screening and Enrollment Visit may take place at a location affiliated with the study site (for example, a satellite clinic).

With the permission of the participant, a physician investigator or designee will be available to answer questions of the primary obstetrician or other clinical care staff regarding the requirements of study participation. Appropriate written materials for clinical care staff members describing study procedures and supporting the correct interpretation of the study protocol will be placed in the participant's prenatal chart after written informed consent has been obtained from the participant.

Participants will be contacted with results of laboratory tests done at the Screening and Enrollment Visit once results are available; all results are likely to be available within approximately one week. Results other than HIV testing may be provided by phone.

**Table 2: Screening and Enrollment Visit**

Screening and Enrollment Visit	
Component	Procedure/Analysis
Administrative	
 
• Obtain written informed consent
 
• Collect locator information
 
• Administer eligibility assessment
 
• Assign Participant ID
 
• Obtain signed records release
 
• Record demographics
 
• Plan for Pharmacokinetic Measures Visit (Date of Planned C/S)
 
• Provide reimbursement for study visit
 

Clinical	
 
• Review prenatal record
 
• Review ultrasound report(s)
 
• Record medical history
 
• Record concomitant medications
 
• Perform targeted physical exam
 
• Perform pelvic exam
 

Laboratory	
 
• Collect pelvic specimens 
 
○ Trichomonas culture
 
○ *Wet prep and vaginal pH
 
○ *Herpes Culture
 
 
 
• Collect urine specimen 
 
○ Urine SDA for chlamydia and gonorrhea
 
 
 
• Collect blood specimen 
 
○ Serum creatinine
 
○ AST and ALT
 
○ Rapid HIV test with pre- and post-test counseling
 
○ *Confirmatory Testing for HIV
 
○ *HBsAg
 
○ *RPR
 
○ *Confirmatory Testing for Syphilis
 
 
 

\*As clinically appropriate

## **7.2 HIV Test Results**

Participants will receive their HIV test results in person in the context of a post-test counseling session with a trained study staff member. As rapid testing will be used, results are expected to be available during the study visit.

In the unlikely event that an indeterminate or positive HIV test result occurs, participants will be informed of their results in person by a physician investigator able to participate in a thorough discussion of follow-up testing and treatment options, including prevention of mother-to-child transmission (PMTCT), as appropriate. Confirmation of HIV infection will occur according to guidelines presented in Appendix II.

If applicable, study staff members will make every effort to refer the participant to appropriate clinical and social support resources for HIV-infected pregnant women.

### **7.3 Pharmacokinetic Measures**

For the purposes of scheduling subsequent evaluation and follow-up, the date of gel administration will be considered Day 0. The time of gel administration will be considered Time 0. Timed pharmacokinetic measures are timed by hours passed since gel administration, not cesarean section.

A physician investigator will not be the primary or first assistant surgeon for the cesarean section. A physician investigator will be responsible for collection of study-related specimens in the operating room.

Flow cytometry for CD38 and CD95 will be obtained pre-dose on Day 0. This will be required as a surrogate for cell activation and proliferation markers, respectively, to serve as covariates in the intracellular model building.

If not already in place, a saline lock (or similar device) will be inserted to facilitate the collection of multiple blood specimens. This device may be replaced as needed in the event of a non-functioning device. Specimens will not be drawn from the site of an ongoing intravenous infusion.

Surgery and anesthesia may contribute to a temporary increase in intravascular volume, though this is often a function of the duration of surgery. Accordingly, there may be an increase in volume of distribution, especially for water soluble drugs, that would transiently reduce drug concentrations in the blood. Drugs used in anesthesia (including their time of administration) and operative time are routinely recorded and these data will be captured.

As the majority of these evaluations are likely to occur in the pre-operative area, operating room, and post-operative areas of the hospital, participants will not receive reimbursement for this study visit in these settings, which are expected to be relatively short-term. Rather, reimbursement will be provided for all study participation that occurs in the inpatient setting at the 24 Hour Evaluation or other setting as needed.

**Table 3: Pharmacokinetic Measures: Gel Administration Day (Day 0)**

Pharmacokinetic Measures		
Component	Procedure/Analysis	
Pre-Gel	Admin.	
 
• Update locator information
 
• Place copy of consent in inpatient chart
 
• Review inpatient chart
 
• Administer eligibility assessment/Confirm eligibility
 
• Schedule next study evaluation
 

	Clinical	
 
• Update medical history
 
• Update concomitant medications
 
• Update adverse events
 
• Perform targeted physical exam
 
• Perform pelvic exam
 

	Lab	
 
• Insert/Replace saline lock or similar (if not already inserted)
 
• Draw blood for:               
 
○ maternal plasma tenofovir level
 
○ flow cytometry
 
 
 

Gel	
 
• Gel administration by study physician
 
	
Post-Gel	C/S	
 
• Amniotic fluid collection
 
• Endometrial tissue collection
 

	Clinical	
 
• Collect adverse events at each PK time point
 
• Review inpatient chart (during 1-12 hours post-gel)
 

	Lab	
 
• Insert/Replace saline lock as needed
 
• Draw blood for maternal plasma tenofovir level               
 
○ 1, 2, 4, 6, 8, and 12 hour time points                   
 
▪ Note: the above time points are after gel administration.
 
▪ Some time points may occur before cesarean section.
 
▪ The allowable window for each blood draw is +/-15 minutes.
 
 
 
 
 
• Cord blood collection               
 
○ may also be collected during cesarean section if possible
 
 
 
• Placental tissue collection               
 
○ may also be collected during cesarean section if possible
 
 
 

## 7.4 24 Hour Evaluation

The 24 Hour Evaluation will occur between 22 and 26 hours following product administration.

**Table 4: 24 Hour Evaluation**

24 Hour Evaluation	
Component	Procedure/Analysis
Administrative	
 
• Update locator information
 
• Schedule Two Week Phone Call
 
• Provide reimbursement
 

Clinical	
 
• Review inpatient chart
 
• Record/Update concomitant medications
 
• Record/Update adverse events
 
• *Perform targeted physical exam
 
• *Perform pelvic exam
 

Laboratory	
 
• Draw blood for maternal plasma tenofovir level
 

\*only as clinically indicated

## 7.5 Two Week Phone Call

The Two Week Phone Call will collect data on any new or outstanding adverse events, as well as other procedures as outlined in Table 5. The window for the phone call is Day 10 to Day 18.

**Table 5: Two Week Phone Call**

Two Week Phone Call	
Component	Procedure/Analysis
Administrative	
 
• Update locator information
 
• Update demographics
 
• *Review inpatient chart
 
• *Review outpatient chart
 
• Trigger staff to send reimbursement for phone call
 
• *Schedule next visit
 

Clinical	
 
• Update concomitant medications
 
• Update adverse events
 

\*as clinically indicated

## 7.6 Unscheduled Visit

An Unscheduled Visit may occur at any time during study participation, and may be triggered by participant report of an adverse event that is unresolved at the 24 Hour Evaluation, or that is reported following the 24 Hour Evaluation.

**Table 6: Unscheduled Visit**

Safety Visit	
Component	Procedure/Analysis
Administrative	
 
• Update locator information
 
• *Sign records release
 
• *Schedule next visit/call
 

Clinical	
 
• Update concomitant medications
 
• Update adverse events
 
• Perform targeted physical exam
 
• *Perform pelvic exam
 
• *Review inpatient chart
 
• *Review outpatient chart
 

Laboratory	
 
• *Serum creatinine
 
• *ALT
 
• *AST
 
• *RPR
 
• *Confirmatory testing for syphilis
 
• *Rapid HIV Test
 
• *Confirmatory testing for HIV with pre-and post-test counseling
 
• *HBsAg
 
• *Maternal plasma tenofovir level
 
• *Urine SDA for CT and GC
 
• *Urinalysis
 
• *Urine culture and sensitivity
 
• *Wet prep and vaginal pH
 
• *Trichomonas culture
 
• *Herpes culture
 
• *Other laboratory tests deemed clinically appropriate, when possible after consultation with the PSRT
 

\*as clinically indicated

## 7.7 Final Contact

In most cases the final contact will be the Two Week Phone Call. If necessary, the study site may complete the final contact visit(s), including the script for the Two Week Phone Call, at the study site or at community based locations, depending on site

capacities and site and participant preferences. All final contacts must be documented in participant study records.

## **7.8 Clinical Evaluations and Procedures**

Clinical evaluation of participants will include a targeted physical exam as described in Appendix III.

## **7.9 Laboratory Evaluations**

### **7.9.1 Local Laboratory**

The local laboratory, site investigator, or designee will run the following, as indicated:

- Serum creatinine
- AST
- ALT
- Rapid HIV test
- Confirmatory testing for HIV
- Hepatitis B surface antigen
- Rapid plasma reagin
- Confirmatory testing for syphilis
- Wet preparation slide
- Vaginal pH
- Herpes culture
- Urinalysis
- Urine culture and sensitivity
- Flow cytometry

### **7.9.2 Network Laboratory**

The Network Laboratory will run the following:

- Urine SDA for chlamydia and gonorrhea
- Trichomonas culture
- Pharmacokinetic analyses (at NL Pharmacology Core)

The following specimens will be collected for pharmacokinetic analyses of tenofovir according to guidelines outlined in the Site SOPs.

- Maternal blood
- Amniotic fluid
- Cord blood
- Placental tissue

- Endometrial tissue

Based on HPTN 050, 64% of measurable samples fell in the 2 to 6 hour sampling window which was the basis for selection of sampling times to maximize capture of peak levels in the blood. Measurable levels were spread almost evenly among the 2, 4, and 6 hour sample times. Subjects' peak tenofovir concentrations occurred throughout this window. In HPTN 050, 38% of measurable levels were after 4 hours so they are somewhat less likely to be measurable, but will be nearly as informative as the 4 hour sample.

MTN-002 will use a more sensitive tenofovir assay than HPTN 050. Our validated liquid chromatography mass spectrometry (LCMS) method has a limit of quantitation (LOQ) of 5 ng/mL, but uses only 50 microliters of fluid. Previous methods have had a LOQ of 3 ng/mL but used 250 microliters. Since assay sensitivity is largely determined by mass in the sample, not concentration, this likely represents a 3 fold improvement in sensitivity if we use a similar volume as in previous studies. To improve even further, we are planning to dedicate 1 mL serum for the blood tenofovir assay to further increase the sensitivity, possibly below 1 ng/mL. This may increase the number of samples quantifiable in the blood assuming similar pharmacokinetics as in HPTN 050.

As stated above, a validated assay for tenofovir in plasma is currently available. Validated assays for tenofovir in endometrial tissue, amniotic fluid and placental tissue have not yet been developed, but are expected to be ready in 2007. Pharmacokinetic samples may be batch shipped from the NL to the NL Pharmacology Core for assay.

The principal parameter of interest after intravaginal dosing will be the AUC. Plasma will also be analyzed for routine pharmacokinetic parameters ( $C_{max}$ ,  $T_{max}$ ).

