HPTN 050 also addressed pharmacokinetics of vaginally administered tenofovir gel. Fourteen of 25 women (56%) with pharmacokinetic results had low, but detectable, serum tenofovir levels (limit of quantitation: 3.0 ng/mL) at some point in the 12 hours after dosing on either Day 0 (following the first dose) or on Day 13 (after daily dosing); three of the 14 had detectable levels on both days. The maximum tenofovir concentrations ( $C_{max}$ ) ranged from 3.0 - 25.8 ng/mL, with no clear dose-concentration relationship identified. For the woman with the 25.8 ng/mL level, this peak level occurred two hours following the dose; the level rapidly declined to 10.9 ng/mL at four hours and was undetectable at 12 hours following the dose. Besides the outlier with the highest tenofovir level, the next highest  $C_{max}$  was 7.1 ng/mL. Considering all women in the PK cohort, the median tenofovir  $C_{max}$  was 3.4 ng/mL (interquartile range: below limit of quantitation [3.0 ng/mL] to 4.7 ng/mL). The median  $C_{max}$  for all subjects (3.4 ng/mL) corresponds to approximately 1% of the maximum ( $C_{max, steady-state (ss)}$ ) and 7% of the minimum (C24 single dose) blood concentrations at steady-state with 300 mg daily oral tenofovir dosing. Findings from CONRAD A04-095 are expected to further inform the pharmacokinetic data on vaginally administered tenofovir gel.

Figure 1 presented below demonstrates tenofovir blood concentration following vaginal administration of tenofovir 1% gel in HPTN 050. All levels for all women with measurable tenofovir levels in the blood are shown. (14 of 25; lower limit of quantitation (LLOQ) approximately 3.0 ng/mL [dotted line]). Legend indicates “cohort” – “ID” – “study day”. For reference the tenofovir level associated with the median 24 hour post-dose blood concentration following an oral 300 mg tenofovir dose is indicated with dashed line.

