### 3.2 Secondary Objectives

- Characterize the systemic safety profile of single-dose tenofovir 1% vaginal gel in term gravidas
- Compare 3rd trimester absorption of tenofovir 1% vaginal gel to absorption in non-pregnant recent historic controls
- Assess amniotic fluid, cord blood, endometrial tissue and placental tissue levels following single-dose tenofovir 1% vaginal gel

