### 10.3 Study Hypothesis

We hypothesize:

- Study hypothesis 1: Plasma absorption in participants will be detectable in a percentage of women similar to that seen in HPTN 050 (approximately 33%)
- Study hypothesis 2: Of women with detectable levels of tenofovir, a small fraction will have detectable levels in endometrium, cord blood, placental tissue, and amniotic fluid

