### 10.4 Sample Size

The power of the study can be characterized as follows: if the overall absorption rate (defined as the proportion of women with detectable levels of PMPA in plasma, endometrium, cord blood, placental tissue, and/or amniotic fluid) was expected to be 33%, 16 women would provide 72% power to exclude absorption rate > 60%. In addition, the lower and upper bounds of the exact 95% confidence interval (CI) around the absorption rate are 13% and 57%, respectively, if the observed number of absorption in a cohort of 16 women was 5 (31%: 5 out 16).

For endpoints where no or very low absorption rates are expected (e.g., endometrium, cord blood, placental tissue, and amniotic fluid), 16 women would provide 80% power to exclude absorption rate > 25% assuming the true rate of absorption is 5%. In addition, the upper bounds of the exact 95% confidence interval (CI) around the absorption rate are 20% and 30% if the observed number of absorption in a cohort of 16 women was 0 or 1, respectively.

Additional participants may enroll in the study, at the discretion of the protocol team, to replace currently enrolled participants who receive study gel but whose time of cesarean delivery is greater than 8 hours following the time of study gel administration. Thus, in the event that participants are replaced for this purpose, the total sample size at the end of the study may slightly exceed 16 participants who received study gel.

A sample size of 16 women is insufficient to provide a formal statistical assessment for the comparison between the plasma absorption level observed in HPTN 050 and the one that will be observed in this study.

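### Hypothesis 1 compares the share of women with detectable plasma tenofovir with a benchmark set at 3.0 ng/mL, but the MTN-002 assay will have a different limit and no common cut-off is set

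*Protocol*

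**What the plan says.** Section 10.3 (also 2.11) states hypothesis 1: "Plasma absorption in participants will be detectable in a percentage of women similar to that seen in HPTN 050 (approximately 33" per cent). Section 10.4 carries the same idea into the sample size. The absorption rate is "defined as the proportion of women with detectable levels of PMPA in plasma, endometrium, cord blood, placental tissue, and/or amniotic fluid", its expected value is 33%, and "16 women would provide 72% power to exclude absorption rate > 60" per cent. Section 3.2 adds a secondary objective to compare third-trimester "absorption of tenofovir 1% vaginal gel to absorption in non-pregnant recent historic controls", without naming a metric.

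Section 2.10 describes the benchmark study. Its limit of quantitation was 3.0 ng/mL. Fourteen of 25 women (56%) had a detectable level "at some point in the 12 hours after dosing on either Day 0 (following the first dose) or on Day 13 (after daily dosing"), and three of the 14 were positive on both days. Median Cmax was 3.4 ng/mL and the upper quartile 4.7 ng/mL.

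Section 7.9.2 says of the new assay: "MTN-002 will use a more sensitive tenofovir assay than HPTN 050". The validated limit is 5 ng/mL on 50 microlitres, against 3 ng/mL on 250 microlitres previously. One millilitre of serum is to be set aside "to further increase the sensitivity, possibly below 1 ng/mL". The same section concedes that more samples may become quantifiable even if pharmacokinetics resemble HPTN 050.

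Section 10.6.2 summarises concentrations with continuous statistics. It switches to the proportion detectable, with a Clopper-Pearson interval, if a substantial number of women fall below the limit.

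**The concern.** Whether a woman is detectable depends on the assay limit as well as on her concentration. HPTN 050 peak values sit almost on the old limit, so a modest shift in the limit reclassifies many women. The protocol accepts that the count may rise with unchanged pharmacokinetics, yet it keeps 33% as both the prediction and the planning rate.

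Section 2.10 hypothesises increased absorption in pregnancy. A higher detectable share caused by the assay could be taken as confirmation of that, and a lower share as evidence against it.

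Three further differences affect the contrast:

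- The HPTN 050 count of 14/25 gives each woman two occasions, one of them after daily dosing. MTN-002 has one dose.
- MTN-002 samples to 24 h; the HPTN 050 count covers 12 h.
- Section 7.3 warns that surgery and anaesthesia may increase distribution volume in a way "that would transiently reduce drug concentrations in the blood".

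**Working it through.** **1. The plan's power figure.** Inputs from section 10.4: n = 16, null rate 0.60, true rate 0.33. Alpha is not stated. With one-sided alpha 0.05 and the normal approximation:

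- SE under the null = sqrt(0.60 × 0.40 / 16) = 0.1225; SE under the alternative = sqrt(0.33 × 0.67 / 16) = 0.1176.
- Power = Φ((0.27 − 1.645 × 0.1225) / 0.1176) = Φ(0.583) = 72.0%, which matches the protocol.
- The exact binomial rule (exclude 60% if at most 5 of 16 are positive, size 1.9%) gives 55.8%. It is used below.

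**2. The benchmark.** Either-day detection is 14/25 = 56%. If all 25 women were sampled on both days (an assumption), the per-occasion rate is (14 + 3)/50 = 34%. This fits the protocol's figure of about 33%, whose basis the protocol does not state.

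**3. The assay limits.** Section 7.9.2 argues that sensitivity depends on the mass in the sample.

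- Previous method: 3 ng/mL × 0.250 mL = 0.75 ng. New method: 5 ng/mL × 0.050 mL = 0.25 ng. The ratio of 3.0 reproduces the stated threefold gain.
- Implied limits are 1.0 ng/mL at 250 microlitres and 0.25 ng/mL at 1 mL. Only 5 ng/mL at 50 microlitres is described as validated.

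**4. Detectable share with unchanged pharmacology.** Assume log-normal Cmax with P(Cmax ≥ 3.0) = 0.33 and log-SD s. Then P(Cmax ≥ L) = Φ((ln 3.0 − ln L)/s − 0.440). The HPTN 050 quartiles give s = ln(4.7/3.4)/0.6745 = 0.48. If they describe the larger of two independent days, s is about 0.575. Larger values allow for a heavier tail. The last two columns are for n = 16 and a limit of 1 ng/mL.

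| s | share at 5 ng/mL | at 3.0 | at 1 | power to exclude >60% | chance that the 95% CI lies wholly above 33% |
|---|---|---|---|---|---|
| 0.48 | 7% | 33% | 97% | about 0 | about 100% |
| 0.575 | 9% | 33% | 93% | about 0 | about 100% |
| 0.8 | 14% | 33% | 82% | about 0 | 99% |
| 1.0 | 17% | 33% | 74% | 0.03% | 91% |
| 1.5 | 22% | 33% | 62% | 1.4% | 58% |

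The Clopper-Pearson lower bound passes 33% from 10 of 16 positives (bound 35.4%). At a 3.0 ng/mL cut-off that chance is 1.5%, and exact power stays at 55.8%. At 5 ng/mL the error reverses: power to exclude 60% rises to 89-99.96%, because the assay misses women whom the old one would have counted.

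**5. A check without the model.** The HPTN 050 upper quartile of 4.7 ng/mL means that at most about a quarter of women reached 5 ng/mL, even counting both days. A fall below 33% at that limit therefore does not depend on the log-normal shape.

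**The case against.** The strongest reply is that the comparison is secondary and descriptive. Section 10.4 says 16 women are too few for a formal assessment against HPTN 050, the primary objective does not depend on it, and the protocol discloses the assay difference. Section 10.6.2 makes continuous summaries the default, so if nearly every woman is detectable, Cmax can be set beside the HPTN 050 median of 3.4 ng/mL. All of this stands. It limits the harm, but hypothesis 1 and the section 10.4 rate remain stated as proportions detectable.

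A reader might infer three stronger claims that the documents do not support:

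- **Unchanged pharmacology must look like a large pregnancy effect.** The limit is only possibly below 1 ng/mL. If the validated 5 ng/mL were kept, the error would run the other way. Two-occasion counting in HPTN 050 and any surgical dilution would also push MTN-002 downward by comparison.
- **A false significant result.** All 16 women against 14/25 gives Fisher p = 0.003, but no such test is planned, 14/25 is the either-day count, and 16/16 is the extreme case. With 13/16, p = 0.18; with 12/16, p = 0.32.
- **Secondary objective 2 is defined by detectability.** Section 3.2 names no metric, so that objective is affected only where it is judged by the detectable share.

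The fitted shape is also open to challenge. With median 3.4 ng/mL and s = 0.48, a value of 25.8 ng/mL or more among 25 women has probability of about 0.0003, yet one was observed. That is why the table runs to s = 1.5.

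**Conclusion.** The point holds for hypothesis 1, for the plasma part of the section 10.4 absorption rate, and for any other comparison with HPTN 050 made on the proportion detectable. With no change in pharmacology, a 33% rate at 3.0 ng/mL becomes about 62-97% at 1 ng/mL or about 7-22% at 5 ng/mL. The contrast then mainly reports the assay limit, and the 72% power statement does not describe the planned measurement. The sizes rest on the log-normal assumption, the 33% anchor and log-SD 0.48 to 1.5; the direction at each limit holds across that range. The consequence is a misleading descriptive reading, not a false-positive test.

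**What to change.** State in sections 10.3, 10.4 and 10.6.2 that, for hypothesis 1, the plasma part of the absorption rate and any detectable-proportion comparison with HPTN 050:

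- A woman is positive only if a plasma concentration is at or above the higher of 3.0 ng/mL and the final MTN-002 limit, within the nominal times up to 12 h common to both studies.
- The benchmark is a single occasion: HPTN 050 Day 0 if those data are available, otherwise the figure of about 33% with its basis stated. The either-day 14/25 is not used.
- If the final limit exceeds 3.0 ng/mL, the HPTN 050 data are re-cut at that limit or the comparison is not made.
- Detection at the new limit is reported separately.
- Samples are flagged as before or after delivery by actual delivery time. Nominal draw time will not do: Table 1 allows gel up to four hours before the expected section, and section 4.5 replaces participants only when delivery is more than 8 hours after gel, so a 2 h or 4 h draw can fall on either side.

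The cost is one extra dichotomisation, a time flag and a smaller like-for-like comparator. No new MTN-002 samples are needed. Access to individual HPTN 050 Day 0 values must be confirmed; the protocol does not say whether they are available.
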